These interviews will inform development of the curriculum for the 3-session I-IMR module on COVID-19 and other viral diseases. This component of the project will also involve development of the primary outcome measure, given that no appropriate measure of COVID-19 knowledge and use of behaviors to avoid catching and spreading disease was available. After finalizing the curriculum for the 3-session I-IMR module, interventionists will be trained to deliver it by phone or video. We will record the sessions to permit supervision and fidelity assessment by the co-developers of I-IMR. All participants have already consented to audiotaping or videotaping of IIMR sessions. Research staff will conduct baseline, 6- and 12-week assessments by phone with all participants (75 I-IMR and 75 CDSMP participants). (Site Coordinators will first complete informed consent to participate in this project, by phone using the procedure described below). We will work with the statisticians from the I'M Well project to complete data analyses.

Site Coordinators will contact individuals who have been randomized to I-IMR and CDSMP to invite them to participate in this component of the project. I-IMR group participants will be offered the 3 session I-IMR module and asked to participate in a phone-based assessment no more than one week prior to receiving the intervention (baseline), a second assessment no more than two weeks after completing the 3 sessions (6 week assessment), and a third assessment approximately 12 weeks after receiving the last session of the module (12 week assessment). CDSMP group participants are receiving usual care, which includes generic supportive telephone calls from agency staff. They will be asked to participate in phone-based assessments on the same schedule as the I-IMR participants. For both groups (I-IMR & CDSMP), Site Coordinators will call participants to review a description of the project in the consent form. Consent to participate will be obtained by phone.

Interventions to be Compared

IIMR (Integrated Illness Management and Recovery vs. CDSMP (Stanford Chronic Disease Self-Management Program)

Overview of Integrated Illness Management and Recovery (I-IMR): I-IMR combines 4 evidence-based psychosocial interventions for SMI: (1) *psychoeducation*, which improves knowledge about

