COVID Component Analyses: The primary outcome is a measure we will create, based in part on a large (n=6000) online survey of knowledge and use of measures to prevent contracting and spreading COVID-19 that was conducted in April in both the US and the UK. This will be measured at baseline, 6- and 12-weeks. Covariance pattern modelling will be used for the analysis, with group (intervention vs. comparison), time (baseline, 6- and 12 weeks) and group*time interaction included in the model, and variance-covariance parameters fully estimated to account for within-subject correlation over time. A significant group*time interaction will indicate superiority of I-IMR over CDSMP. In addition to the measures used to evaluate the primary and secondary aims, we will also administer the PHQ-9,¹²¹ the GAD-7,¹²² and the Fear of COVID Scale¹²³ to assess depression, anxiety, and fear of COVID as potential co-variates in the analyses.

Power analysis: The primary outcome is continuous, thus power analysis will be based on a linear mixed model. With n=150 (75 per arm), 3 assessments, assuming 10% attrition, within-subject correlation of 0.05, 2-tailed test with alpha = 0.05, the study has 80% power to detect an effect size of 0.46, between small (0.2) and medium (0.5).

Quantitative Assessment Measures

Table 1. Study Measures

| Aim 1: Physical Illness Self- Management and Activation | Instrument | Baseline | 8 wks | 4 mo. | 8 mo. | 12 mo. |
|--|---|----------|-------|-------|-------|--------|
| Medical Illness Self- Management | Self-Rated Abilities for Health Practices ⁷⁷ | ✓ | | ✓ | ✓ | ✓ |
| Consumer Activation | Patient Activation Measure (PAM) ⁷⁸ | ✓ | | ✓ | ✓ | ✓ |
| Self-Reported Physical Health Functioning | PROMIS Global Health measure ⁷⁹ | ✓ | | ✓ | ✓ | ✓ |
| Social Functioning Scale | Social Functioning Scale ¹¹⁴ | ✓ | | ✓ | ✓ | ✓ |
| Aim 2: Mental Health Self-Management and Activation | | | | | | |
| Psychiatric Illness Self- Management | Illness Management and Recovery Scale ⁸⁰ | ✓ | | ✓ | ✓ | ✓ |
| Consumer Activation | Patient Activation Measure - Mental Health ⁸¹ | ✓ | | ✓ | ✓ | ✓ |
| Self-Reported Mental Health Functioning | PROMIS Global Health measure ⁷⁹ | ✓ | | ✓ | ✓ | ✓ |
| Aim 3: Service Use and Mortality Risk | | | | | | |
| Mortality Risk | ACC/AHA Cardiovascular Risk Score ⁸² | ✓ | | ✓ | ✓ | ✓ |
| Service Use | Number of Hospital Days and ER visits and Cornell Service Index | ✓ | | ✓ | ✓ | ✓ |

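### COVID component: the stated 80% power at an effect size of 0.46 does not follow for the planned group-by-time test at correlation 0.05 if 0.46 is in outcome SDs; the correlation, effect-size scale and contrast need to be confirmed

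*Combined protocol and SAP*

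**What the plan says.** All of this is in section 4, Analysis, in the paragraphs on the COVID component and its power analysis, unless noted.

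- **Schedule.** The primary outcome is a new measure of knowledge and preventive behaviour. On timing the plan says: "This will be measured at baseline, 6- and 12-weeks".
- **Model.** A covariance pattern model is planned, "with group (intervention vs. comparison), time (baseline, 6- and 12 weeks) and group*time interaction included in the model", with the covariance parameters fully estimated.
- **Deciding test.** "A significant group*time interaction will indicate superiority of I-IMR over CDSMP".
- **Power inputs.** "With n=150 (75 per arm), 3 assessments, assuming 10% attrition", then "within-subject correlation of 0.05, 2-tailed test with alpha = 0.05, the study has 80% power to detect an effect size of 0.46".
- **Benchmarks.** The effect is described as "an effect size of 0.46, between small (0.2) and medium (0.5").
- **Timing of the first follow-up** (section 3, Study Design): "a second assessment no more than two weeks after completing the 3 sessions (6 week assessment"). The last assessment comes about 12 weeks after the final session.

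The power sentence does not name the SD that divides the effect, the contrast, the effects assumed at 6 and 12 weeks, or how attrition enters. The only definition of effect size elsewhere is in the main trial's subgroup text in section 4. It divides the estimate by a standard deviation without saying which one.

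**The concern.** A group-by-time test compares changes from baseline. When the within-subject correlation is only 0.05, a change score is nearly as noisy as the difference of two independent measurements: its variance is 2(1 - 0.05) = 1.9 times the outcome variance. A difference of 0.46 outcome SD is then hard to detect with 75 per arm, and 80% looks too high.

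This sentence is the plan's only statement of what the COVID comparison can detect. Section 9 justifies the sample by retention in the main trial and gives no effect size. As printed, a reader cannot tell whether the component was planned around 0.46 or 0.63 outcome SD, whether the correlation is misprinted, or whether power at 0.46 is nearer 50%. A null result would be read differently in each case. The outcome is newly built, so there is no established SD or correlation to fall back on.

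**Working it through.** **Inputs from the plan.** 75 per arm; visits at baseline, 6 and 12 weeks; 10% attrition, so 75 x 0.9 = 67.5 per arm if dropouts contribute nothing; correlation r = 0.05; two-sided alpha 0.05; effect 0.46.

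**Assumptions added here.** Equal correlation between all visits, outcome SD 1, normal approximation, and a free group difference at baseline, as in the planned model.

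**Formula for the planned test.** Let d6 and d12 be the group differences in change from baseline, in outcome SDs, with n per arm. The noncentrality of the 2-df test is

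ncp = n / [3(1 - r)] x (d6² + d12² - d6·d12),

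referred to a noncentral chi-square with cut-off 5.99. Power of 80% needs ncp of about 9.63.

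**Step 1: what reproduces the printed figure.**

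- *Correlation 0.5, outcome SDs, effect sustained at both follow-ups:* ncp = 67.5 / 1.5 x 0.2116 = 9.522. Power is 79.5% and the detectable effect 0.463.
- *Change-score SDs, correlation 0.05:* 0.46 x √1.9 = 0.634 outcome SD. ncp = 67.5 / 2.85 x 0.634² = 9.522, so again 79.5%. On this scale the correlation cancels, which is why the two routes give the same number.
- *Plain two-group comparison at one time point, 75 per arm:* detectable effect 2.8016 x √(2/75) = 0.457, and power at 0.46 is 80.4%. With 67.5 per arm it is 76.2%. This route uses neither the correlation nor the three visits, and it is not the planned test.

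**Step 2: outcome SDs with the printed correlation of 0.05.**

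- *Sustained effect (0.46, 0.46):* ncp = 67.5 / 2.85 x 0.2116 = 5.01. Power is 50.5%, detectable effect 0.64.
- *Linear build (0.23, 0.46):* ncp = 67.5 / 2.85 x 0.1587 = 3.76. Power is 39.3%, detectable effect 0.74.

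These two bracket every profile in which the larger follow-up effect is 0.46 and the other lies between 0 and 0.46. The bracket d6² + d12² - d6·d12 is largest when the smaller effect is 0 or 0.46, and smallest when it is half.

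**Step 3: attrition handling and other contrasts (outcome SDs, r = 0.05).**

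| Test | 67.5 completers per arm | Dropouts' partial data kept | No attrition, 75 per arm |
|---|---|---|---|
| 2-df group-by-time (linear to sustained) | 39-50% | 41-54% | 43-55% |
| 1-df change, baseline to 12 weeks | 49% | 51% | 53% |
| 1-df mean follow-up minus baseline, sustained | 61% | within 61-66% | 66% |

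No entry reaches 80%. For the 2-df test with 67.5 per arm and a sustained effect, the correlation needed for 80% is 0.51.

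**Step 4: a fading effect.** The 6-week visit falls soon after the sessions, so the effect could be larger there. With 0.46 at 12 weeks, 80% power would need a 6-week effect of 0.73.

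**The case against.** The strongest reply is that the printed figure can be reproduced. A group-by-time effect is a difference in change, so dividing by the SD of change is a natural choice, and the printed inputs then give 79.5%. The benchmarks of 0.2 and 0.5 do not settle the scale. A reader might infer from Step 2 that 80% is simply an error, or that the component has been shown to be underpowered. The documents do not support that, because they never say which SD was used. Nor do they establish that 0.05 is a misprint for 0.5: no other correlation is given for this outcome, and the match at 0.5 is numerically identical to the change-score match.

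The reply does not remove the point. On the change-score scale the listed correlation plays no part in the power, and 0.46 becomes 0.63 outcome SD. That is above 0.5, so on the outcome scale it is no longer between small and medium. The single-time-point route leaves the listed attrition unused and would mean that the powered contrast differs from the planned test.

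Two further objections stand in part. A narrow 39-50% holds only if dropouts are lost entirely; the planned model can use their available visits, so about 39-55% is the fair range. The low end depends on a linear build, which the visit schedule does not favour, so the sustained-effect figures are the ones to lead with. It is also true that 150 is an input to the calculation, and that a null result will have its own confidence interval.

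**Conclusion.** The stated inputs and the stated power need correcting or qualifying. If 0.46 is in outcome SDs, the planned test at correlation 0.05 has about 50% power for a sustained effect with 67.5 per arm. Across the time courses bracketed above and the different ways of handling attrition, the range is about 39-55%. The averaged contrast reaches at most about 66%. The effect detectable with 80% power is about 0.64 rather than 0.46 (2-df test, sustained effect, 67.5 per arm).

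The outcome-SD scale is an assumption. It is the usual sense of the benchmarks the plan cites and the scale on which the listed correlation affects power, but the plan does not state it. The other assumptions are equal correlation between visits and a larger follow-up effect of 0.46. About 80% is recovered, for a sustained effect, if the correlation is 0.5 or if 0.46 is in change-score SDs. The documents cannot separate these explanations, so confidence in any single cause is limited. The point is worth fixing because it affects how a null COVID result is read; it does not affect the conduct of the trial.

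**What to change.** 1. Check the correlation against the original calculation. If 0.05 is a misprint for 0.5, correct it; the 80% at 0.46 then stands for a sustained effect.
2. If 0.05 is right and 0.46 is in outcome SDs, restate the figure for the planned group-by-time test: about 50% power at 0.46, or 80% power at about 0.64 outcome SD, for a sustained effect with 67.5 per arm.
3. If 0.46 is in change-score SDs, say so and give its equivalent of 0.63 outcome SD at correlation 0.05.
4. In every case, name the contrast, the effects assumed at 6 and 12 weeks, and the attrition handling. If a single-time-point comparison was the source, replace it with a figure for the planned test. Figures for a linear build are optional.

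The cost is a few sentences and numbers. No participant, visit or analysis changes. The downside is that the stated figure may become less favourable.
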